4.1 Number of Subjects

A formal sample size calculation was not performed for this study. The sample size is based on what was considered an adequate number of subjects for a pilot study to obtain sufficient information on the safety and effectiveness of KB103. Enrolled up to 12 subjects (including Phase I and Phase II).

5 Study Populations

The primary population for an analysis of the proof of mechanism is the intent-to-treat (ITT) population. Study populations are defined in the following sections.

5.1 Analysis Populations

5.1.1 Intent-to-Treat (ITT) Population

The intent-to-treat (ITT) population includes subjects who were administered KB103 who have had at least one paired assessment of the target wound area post-administration, i.e., at least one KB103 target wound and one placebo target wound.

5.1.2 Safety Population

This population is defined as all subjects who were administered KB103.

5.1.3 Per-Protocol Population

The per-protocol (PP) population is defined as all subjects in the ITT population who have had at least one paired assessment of the target wound area post-administration and completed the protocol as planned.

6 Overall Statistical Considerations

6.1 General Conventions

The following general comments apply to all statistical analyses and data presentations:

- Summaries will include frequency and percentages for categorical data; frequency and median for ordinal data; and frequency, mean, standard deviation, and median, minimum, and maximum for quantitative data.
- Duration variables will be calculated using the general formula (end date – start date) +1.
- Change from baseline will be calculated for each subject at the specified time point as the value at the specified time point minus the baseline value.
- Individual subject listings of all data represented on the eCRFs will be provided to facilitate the investigation of tabulated values and to allow for the clinical review of all efficacy and safety parameters.
- Version 9.1.3 (or higher) of SAS® statistical software package will be used to provide all summaries, listings, graphs, and statistical analyses.

6.2 Baseline Definition

In general, baseline is defined as the value closest to, but prior to, administration with either KB103 or placebo.

6.3 Handling of Missing Data

Missing data will be handled as outlined below:

- All missing and partial dates for adverse events or for medications received after randomization will be queried for a value. If no value can be obtained, substitutions will be made as detailed in [Appendix 2](#). These substitutions will be used in calculations; however, the actual value recorded on the eCRF will be used in all listings.
- Missing primary endpoints, values after the last non-missing value would be replaced by the last recorded observed value. This is analogous to a last observation carried forward (LOCF) strategy for study discontinuations. For all the other endpoints, the missing values will not be imputed.
- The severity and causality assessment for adverse events cannot be missing. Missing data will be queried for a value.

7 Statistical Analysis Methods

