## 10.7 Handling of Missing and Incomplete Data

For efficacy evaluation, the treatment endpoint is defined as one assessment time point, which includes the last measurement obtained during the study for a variable. No other imputation of values for missing data is performed. Standard clinical monitoring and data management practices are used to ensure the integrity of data.

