2.2 Study Objectives Phase II

2.2.1 Primary

- 8) To assess wound closure through post-administration imaging:
 - a. To assess proportion of complete wound closure of B-VEC treated wounds to that of placebo treated wounds at weeks 8, 10 and 12.
 - b. Time to wound closure of a KB103-administered wound relative to a placebo-administered wound
 - c. Duration of wound closure of a KB103-administered wound relative to a placebo-administered wound

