8.1.2 Time to Wound Closure

The time to wound closure defined as the time from the first treatment to complete wound closure ($\geq 90\%$ reduction in wound surface from baseline for 2 consecutive weeks) will be summarized by treatment and compared using analysis of variance with treatment as the fixed effect. This analysis will be performed for both Observed and LOCF imputed ITT populations

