8.1.3 Duration of Wound Closure

The duration of wound closure, defined as the time from the complete wound healing to the first reduction in wound surface from baseline to a value below 90%, will be summarized will be summarized by treatment and compared using analysis of variance with treatment as the fixed effect. This analysis will be performed for both Observed and LOCF imputed ITT populations

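### In the LOCF runs of time to closure and duration of closure, one closed reading before exit becomes a confirmed closure that cannot end, and the SAP does not say whether the LOCF or the Observed run leads

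*SAP*

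**What the plan says.** SAP 6.3 sets the missing-data rule: "Missing primary endpoints, values after the last non-missing value would be replaced by the last recorded observed value". It explains: "This is analogous to a last observation carried forward (LOCF) strategy for study discontinuations". Endpoints that are not primary are left unimputed.

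SAP 2.2.1 lists both closure outcomes among the Phase II primary objectives: "Time to wound closure of a KB103-administered wound relative to a placebo-administered wound" and "Duration of wound closure of a KB103-administered wound relative to a placebo-administered wound".

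SAP 8.1.2 defines closure as at least a 90% "reduction in wound surface from baseline for 2 consecutive weeks" and compares treatments by analysis of variance. SAP 8.1.3 counts duration from healing until the reduction first drops under 90%, again with analysis of variance. It adds: "This analysis will be performed for both Observed and LOCF imputed ITT populations". Section 8.1.2 ends with the same sentence. Neither section ranks the two runs. By contrast, SAP 8.1.1 rests on the observed ITT data, and 8.1.1.1 offers the PP and LOCF analyses as sensitivity analyses.

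Protocol 10.7 takes the last measurement as a single treatment endpoint and then says: "No other imputation of values for missing data is performed". Protocol 4.1 and 5.5 are built on re-opening: when a closed wound re-opens, Observation Period 1 ends and Cycle 2 begins.

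**The concern.** Both definitions depend on what happens after the first closed reading. The two-week requirement screens out brief closures, and the duration depends on seeing the wound open again. Carrying a value forward removes both checks. If the last reading before exit is the first at or above 90%, its copy meets the two-week requirement, and further copies can never fall below 90%.

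These are two of the three Phase II primary objectives in the SAP, and the LOCF result stands beside the Observed result with equal rank. The SAP introduction says the plan was written after a partial analysis of an unblinded study, so an unranked pair of results leaves room to choose between them. With up to 12 subjects (SAP 4.1), a single long imputed duration can visibly move an arm's mean.

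A related gap lies in SAP 8.1.1.1. The PP population requires completion of the protocol (SAP 5.1.3), so it leaves withdrawn subjects out. LOCF is then the only sensitivity analysis that assigns them an outcome at weeks 8, 10 and 12.

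**Working it through.** The documents give no power, event-rate or dropout figure for these endpoints, so there is no stated figure to reproduce. The check applies the SAP's own rules to example wounds.

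**Inputs from the SAP.** LOCF after the last observed value (6.3); closure at 90% or more for two consecutive weeks (8.1.2); end of closure at the first value under 90% (8.1.3); duration = (end − start) + 1 (6.1).

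**Assumptions.** Readings every two weeks to week 12, with two successive readings at or above 90% taken as confirmation. The series stops at week 12 (Day 84), because the SAP gives no end date for a wound that never re-opens.

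**Step 1: confirmation.** Percent reduction at weeks 2, 4, 6, 8, 10, 12; a dash means after exit.

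| Series | Observed run | LOCF run |
|---|---|---|
| 20, 50, 70, 92, –, – | not confirmed | confirmed at week 8, no re-opening |
| 20, 92, –, –, –, – | not confirmed | confirmed at week 4, no re-opening |
| 20, 50, 92, 60, –, – | not confirmed | not confirmed |
| 20, 50, 70, 80, 85, 92 | not confirmed | not confirmed |

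The third row shows that the effect needs a last observed value of at least 90%. The fourth shows the asymmetry: a subject who stays to week 12 and first reaches 90% there is not confirmed, while one who reaches 90% and leaves is.

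**Step 2: duration.** A carried series has no value under 90%, so the ending event in 8.1.3 never occurs. Either the duration is undefined and the wound drops out of the analysis of variance, or an end date must be invented. With the assumed week 12 cut:

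- Single closed reading at week 4: (12 − 4) × 7 + 1 = 57 days.
- Week 6: 43 days. Week 8: 29 days. Week 10: 15 days.
- Last image on Day 14, exit on Day 15: 84 − 14 + 1 = 71 days, of which 84 − 14 = 70 fall after the last image.

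**Step 3: how optimistic the carried value is.** The documents give no re-opening rate, so let q be an assumed weekly probability of re-opening.

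| q | Still closed after 1 week, 1 − q | Closed throughout 4 weeks, (1 − q)^4 |
|---|---|---|
| 0.05 | 0.95 | 0.81 |
| 0.10 | 0.90 | 0.66 |
| 0.20 | 0.80 | 0.41 |
| 0.30 | 0.70 | 0.24 |
| 0.50 | 0.50 | 0.06 |

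LOCF sets every entry to 1. Equivalently, with an assumed median time to re-opening of 4, 8 or 16 weeks, the chance of unbroken closure over 8 weeks is 2^(−8/4) = 25%, 2^(−8/8) = 50% or 2^(−8/16) = 71%.

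**Step 4: direction.** A subject's KB103 and placebo wounds stop being observed together, so LOCF freezes their difference as it stood at exit. The arm with more wounds closed at that moment gains.

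**Step 5: scope.** In Phase I both outcomes are secondary (SAP 2.1.2), so 6.3 would not impute them. Sections 8.1.2 and 8.1.3 nevertheless apply LOCF without separating the phases.

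**The case against.** The strongest reply is that every analysis in 8.1.2 and 8.1.3 is also run on observed data, which this mechanism does not touch, and that subject listings are planned. A reader might infer that the LOCF figure is the endpoint result; the SAP does not say so. This reply stands as a limit on the point, but it does not remove it, because the SAP does not say which run leads.

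Several other stronger readings also fail:

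- *That LOCF favours KB103.* The documents do not fix the direction.
- *That LOCF is the only sensitivity analysis for healing at weeks 8, 10 and 12.* The PP analysis is another, though it deals with withdrawals only by leaving them out.
- *That the SAP yields 71 days.* It yields no end date; Day 84 is an assumption, and exit the day after a single closed image is an extreme case, since imaging is planned every 2 to 3 days in the observation periods.
- *That 25%, 50% and 71% are true healing rates at weeks 8, 10 and 12.* They describe unbroken closure. Healing at those weeks is status on the day, and a wound can re-open and close again.
- *That LOCF contradicts the design.* It is an optimistic assumption in a study that expects re-opening. Protocol 10.7 itself uses the last measurement, but as one endpoint and not to fill a weekly series.

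It is also fair to say that a wound still closed at its last image has no end date in the Observed run either, so deleting LOCF alone would not settle duration. Finally, no dropout rate is given. Withdrawal at any time and roll-over to Phase 3 are allowed, but nothing shows that either will happen before week 12.

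**Conclusion.** The point holds for the LOCF runs of 8.1.2 and 8.1.3. By the SAP's own definitions, a last observed value that is a first reading of at least 90% is turned into a confirmed closure with no possible end. That conclusion needs no outside figure beyond reading the carried values as filling the following weeks. The size is conditional: an imputed duration of 15 to 57 days for a single closed reading at week 10 down to week 4, and 71 days for Day 14, all under the assumed week 12 cut. How many wounds would be affected cannot be known from the documents. The point does not show that the Observed results are biased in this way, or that KB103 gains. It deserves correction because the affected run has equal standing on two primary objectives of a very small study.

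**What to change.** 1. Delete the LOCF runs from SAP 8.1.2 and 8.1.3, which leaves the observed data as the sole basis and settles which run leads.
2. State in 8.1.2 that both confirming weeks must be observed.
3. Censor time to closure and duration of closure at the last image actually taken. This also covers wounds still closed when observation ends.
4. Replace the analysis of variance, which cannot use censored times, with a method that accepts censoring and keeps the within-subject pairing, for example Kaplan-Meier summaries with a comparison stratified by subject.
5. In 8.1.1.1, add a sensitivity analysis that sets both wounds to not healed at every scheduled week after exit, shown beside the LOCF result.

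The cost is SAP wording, a change of method for two endpoints and one extra table; no new data are needed. The figures may move in either direction. With up to 12 subjects the stratified comparison will have few informative pairs, especially for duration, where a subject contributes only if both a KB103 and a placebo wound closed. The summaries may therefore have to carry most of the message.

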7.1 Subject Disposition

The number of subjects included in each of the analysis populations (ie, ITT, Safety and PP) will be summarized by treatment group. A listing will be provided that indicates each subject's inclusion in/exclusion from the populations and the reason for exclusion from each of the populations.

The number and percentage of subjects completing the study (defined as receiving at least 1 administration of either treatment (KB103 or placebo) and returning for weeks 8, 10, and 12, not completing the study, and prematurely discontinuing from treatment will be presented for the ITT, safety and PP populations. A listing of all subjects who prematurely discontinued from treatment or not completing the study will be presented, and the primary reason for discontinuation of treatment or not completing the study will be provided.

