### 5.4.2 At-home Procedures

After the first administration of each cycle, KB103 may be administered at home by a caretaker every 2 to 3 days until wound closure, a stopping criterion is met, 3 months have elapsed, or until directed to discontinue by the Investigator.

Appendix 1 provides administration instructions. Wound closure is monitored through remote imaging.

### 5.4.3 Last Dosing Day of Cycle 1

The patient will visit the Investigative site on or near the final Cycle 1 administration day, in which the following procedures will be performed:

- Collection of blood (approximately 10 mL) for clinical laboratory tests:
  - Serum chemistry
  - Hematology
  - Viral shedding
  - HSV and COLVII autoantibodies
- Collection of urine for viral shedding
- Optional: biopsy collection from a wound area
- Wound stenciling
- Topical administration of KB103 and placebo to the target areas

## 5.5 Observation Period (OP) 1

Following Cycle 1 wound closure and/or 3 months, the patient returns home. Wound areas are imaged every 2 to 3 days at home with a phone app.

The duration of OP 1 varies. If complete wound closure is obtained during Cycle 1, OP 1 ends when the wound(s) re-open. If complete closure is not obtained during Cycle 1, OP 1 ends when the wound surface area increases relative to size of the wound at the last Cycle 1 administration.

## 5.6 Cycle 2

The patient will visit the Investigative site for the first dose of Cycle 2. Additional Cycle 2 doses can occur on-site or at-home at the discretion of the Investigator. For Cycle 2, KB103 and placebo are administered topically every 2 to 3 days to correspond with bandage changes, up to 3 months.

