### 10.5.3 Target Wound Area

Target wound surface area is obtained through on-site and at-home imaging of target areas. Change in area from baseline is evaluated for using a paired t-test for each KB103 target wound vs. control wound.

Time to closure and durability of closure will be assessed after each cycle of administrations.

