The efficacy objective is the proportion of DEB wound sites with complete wound healing from baseline ($\geq 90\%$ reduction in wound surface from baseline) in KB103 versus placebo treated intra-participant wound sites at Weeks 8, 10 and 12 as determined by the Investigator.

The number and percentage of subjects in each treatment group defined as Complete Wound Healing (CWH) will be tabulated. The null and alternative hypotheses are as follows:

Null Hypothesis $H_0: \%CWH \text{ in KB103} = \%CWH \text{ in Placebo}$

Alternate Hypothesis $H_1: \%CWH \text{ in KB103} > \%CWH \text{ in Placebo}$

Where $\%CWH$ is the percentage of wounds with a complete wound healing from baseline at week 8, 10 and 12. A one-sided significance level of 0.05 is considered

The objective of the proportion of DEB wound sites with complete wound healing from baseline ($\geq 90\%$ reduction in wound surface from baseline) will be analyzed using the Cochran-Mantel-Haenszel (CMH) test stratified by the time points (weeks 8, 10 and 12). Under the null hypothesis of no association between complete wound healing and treatment, this test statistic follows a chi-square distribution with 1 degree of freedom. The CMH test provides test of independence for the repeated evaluations at weeks 8, 10 and 12.

In addition to testing the null hypothesis, the CMH test also provides an estimate of the common odds ratio to summarize how large the treatment effect is when pooled across the different weeks of the treatment assuming the odds ratio is the same in the different weeks of treatment. This assumption will be tested using the Breslow-Day test and corresponding p-values will be provided. The null hypothesis of the CMH test is that the odds ratios within each week are equal to 1, indicating the complete wound healing proportions are the same.

A summary table with individual treatment proportions and the p-values treatment effect resulting from the chi-square test will be provided. In addition, p-values for independence of weekly evaluations (weeks 8, 10 and 12) using the Breslow-Day test will be provided.

8.1.1.1 Sensitivity and Supplemental Analyses of the Change in Wound Surface Area:

- The analysis performed in Section 8.1.1 for the efficacy objective will be repeated for the PP and LOCF imputed ITT populations.

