11.1 Appendix 1: Schedule of Events

11.1.1 Protocol Version 1.0

Visit	Prescreen	Screen	1	2	3 ¹	4 ²	5				
Week	N/A	-2	0	2	4	6	12				
Day	N/A	-14	0	2	14	28	30	42	84		
Event	Window	N/A	± 2wk	N/A	N/A	± 2d	± 2d	N/A	± 2d	± 5d	LTFU
KB103 Administration ³			X	X	X	X					
Placebo Administration			X	X		X	X				
Phone Screen	X										
ICF / Assent / HIPAA		X									
Inclusion / Exclusion Criteria	X	X	X								
Demographics	X	X									
Medical / Medication History	X	X	X								
Concomitant Medications			X	X	X	X	X	X	X	X	
Adverse Events			X	X	X	X	X	X	X	X	
Physical Exam			X	X						X	
Vital Signs		X	X	X	X	X	X	X	X	X	
Digital Imaging of Wounds ⁴		X	X	X	X	X	X	X	X	X	
Wound Assignment		X									
Pre-dose tattoos		X									
Bacterial Culture										As Needed	
Blood and Urine Tests	Urine Pregnancy Test		X	X							
	Hematology & Chemistry		X	X		X			X	X	
	HIV, Hep B, Hep C Testing		X								
	RCV evaluation		X		X						
	COL7 Antibody Assay ⁵		X		X				X		
	HSV Antibody Assay ⁵			X	X				X		
	Viral shedding assay, urine ⁶		X	X	X	X	X	X	X	X	
	Viral shedding assay, blood ⁶		X	X	X	X	X	X	X	X	
	Genetic Testing	X ⁷									
Day		PS	S	0	2	14	28	30	42	84	
Wound Biopsies	IF for COL7				X	X			X	X	
	qRT-PCR for mRNA and qPCR for viral vector DNA ⁸				X			X			
	IEM for Anchoring Fibrils					X			X	X	
Intact Skin Biopsies	IF for COL7		X ⁷	X ⁷	X	X	X		X	X	
	qRT-PCR for mRNA and qPCR for viral vector DNA ⁸		X ⁷	X ⁷	X	X		X			
	IEM for Anchoring Fibrils		X ⁷	X ⁷	X		X		X	X	

 = Perform the procedure before and after dosing.

 = Optional biopsy. Reference Section 7.2.

¹ If the target wound is closed at Day 28, do not administer KB103 topically.

² If the target wound is closed at Day 28 and then reopens by Day 42, topical KB103 is re-administered at this visit.

³ Topical and intradermal KB103 administration. Skin must be tattooed prior to administration.

⁴ On dosing days, image the KB103 and control wounds both pre- and post-dose.

⁵ May be waived at Day 84 if prior results are negative.

⁶ On dosing days, collect viral shedding samples both pre-dose and 2 hours post-dose.

⁷ Only if needed for diagnosis.

⁸ mRNA and DNA biopsies will minimized to the extent possible (based on previous knowledge) in children

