11.1.3 Protocol Version 3.1

Visit	1			2	3	4		
Day	0/Screen/BL ¹	1	3	15	30	60 ²	90	91-180 ³
Genetic Testing	X							
Bacterial Culture ⁴	X	X		X	X	X	X	X
Urine Pregnancy Test ³	X	X				X		
HIV, Hep B, Hep C Testing ³	X	X				X		
Hematology & Chemistry ⁵	X				X		X	X
COL7 Antibody Assay ⁴	X				X		X	
HSV Antibody Assay ⁶	X				X		X	
Wound Assignment	X							
Pre-dose tattoos	X							
Concomitant Medications		X	X	X	X	X	X	X
Adverse Events		X	X	X	X	X	X	X
Viral shedding (skin swab)	X	X	X	X	X	X	X	X
Physical Exam	X						X	
PRO Assessment	X				X	X	X	X
Global Wound Assessment	X				X	X	X	X
Vital Signs	X				X	X	X	X
At-home wound imaging ⁷							X	
On-site wound imaging	X	X	X	X	X	X	X	
At-home topical IP administration							X	
On-site topical IP Administration					X	X	X	X
ID KB103 admin to intact skin ⁸					X			
Intact skin biopsy ⁹					X	X	X ⁹	X
Wound biopsy ¹⁰	X				X	X	X	X
X	Optional procedures. Early results may negate the need for ID injection and biopsies to intact skin in later patients.							

¹ Diagnostic screening procedures can be performed prior to the visit as indicated below

² Day 15 and 60 visits are required for patients that receive ID injections to intact skin at Day 1.

³ Follow-up visits after Day 90 are conducted as the subject is able at the discretion of the Investigator

⁴ Conducted as clinically indicated

⁵ After screening/baseline, performed only as clinically indicated to minimize blood draws

⁶ May be waived after the first follow-up visit if prior results are negative.

⁷ Subjects will be instructed to image the target wounds during bandage changes (approximately twice per week). ⁸ Optional ID administration for subjects at least 13 years old. Performed at the discretion of the Investigator. Early results may negate the need for ID injection and biopsies to intact skin in later patients.

⁹ Two intact skin locations will be biopsied on Day 30

¹⁰ Biopsies are performed at the discretion of the Investigator and Sponsor.

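### SAP 7.1 makes completing the study depend on a week-10 return that the v1.0, v2.2 and v3.1 schedules do not list, so on listed visits 0 of their 11 subjects can be completers

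*SAP*

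**What the plan says.** SAP 7.1 defines completing the study as "receiving at least 1 administration of either treatment (KB103 or placebo) and returning for weeks 8, 10, and 12". It reports the number and percentage completing for the ITT, safety and PP populations, and asks for a listing that gives the primary reason for every subject who did not complete.

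The PP population in SAP 5.1.3 is described separately, as ITT subjects with a "paired assessment of the target wound area post-administration and completed the protocol as planned".

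The same three weeks return in SAP 8.1.1, where the efficacy objective compares "intra-participant wound sites at Weeks 8, 10 and 12 as determined by the Investigator" and the CMH test is stratified by week. SAP 7.3 also uses them to summarise exposure.

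The visit schedules are in SAP Appendix 1, one per protocol version:

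- **v1.0:** visits on Days 0, 2, 14, 28, 30, 42 and 84, labelled up to weeks 6 and 12. Imaging is tied to these visits; for dosing days a footnote adds "On dosing days, image the KB103 and control wounds both pre- and post-dose". There is no home-imaging row.
- **v2.2:** Days 0 to 5, 30, 60 and 90, then an open period of Days 91-180.
- **v3.1:** Days 0, 1, 3, 15, 30, 60 and 90, then Days 91-180 at discretion. A footnote says "Day 15 and 60 visits are required for patients that receive ID injections to intact skin at Day 1".
- **v4.0:** cycles and observation periods, with no numbered weeks.

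For v2.2 and v3.1 the footnotes add home imaging: "Subjects will be instructed to image the target wounds during bandage changes (approximately twice per week". Protocol 10.5.3 accepts both sources: "Target wound surface area is obtained through on-site and at-home imaging of target areas".

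**The concern.** The definition joins its three returns with *and*, so missing any one of them makes a subject a non-completer. If a version's schedule contains no visit in one of those weeks, a subject who attends everything asked of them still fails the definition.

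Two outputs would suffer. The disposition table would report non-completion that reflects the rule and not the subject's conduct. The listing would need a primary reason for each such subject, and for an adherent subject there is no true reason to enter. The table would also look odd beside the PP column, because subjects placed there for finishing their protocol would be shown as not finishing the study.

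A smaller matter follows from the same weeks. They are the strata of the lead efficacy test, yet the SAP has no rule that assigns a clinic visit or a home image to a week, or that chooses between several. SAP section 1 says the plan was prepared after a partial analysis of a study that is not blinded, so it is better not to leave that choice open.

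**Working it through.** **Inputs.** Subjects by version come from the table in SAP section 3: v1.0 has 2, v2.2 has 4, v3.1/v3.2 has 5, and 3 are planned for v4.0. Visit days come from SAP Appendix 1. The documents give no completion figure to reproduce.

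**Subjects under the first three schedules.** 2 + 4 + 5 = 11. This is 11/12 = 92% of the 12 that SAP section 3 reports as treated, or 11/14 = 79% of the 14 planned (11 + 3).

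**Target days.** Day = 7 × week. The v1.0 schedule confirms the convention by labelling Day 42 as week 6 and Day 84 as week 12. Weeks 8, 10 and 12 are therefore Days 56, 70 and 84. If counting starts at Day 1 (v2.2 lists its first dose there), they are Days 57, 71 and 85.

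**Distance from each target to the nearest listed visit** (Day-1 count in brackets):

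| Version | Week 8 | Week 10 | Week 12 | Separate returns available |
|---|---|---|---|---|
| v1.0 | Day 42: 56 − 42 = 14 (15) | Day 84: 84 − 70 = 14 (13) | Day 84: 0 (1) | 1 of 3 |
| v2.2 | Day 60: 60 − 56 = 4 (3) | Day 60: 70 − 60 = 10 (11) | Day 90: 90 − 84 = 6 (5) | at most 2 of 3 |
| v3.1 | Day 60, not required of all: 4 (3) | Day 60: 10 (11) | Day 90: 6 (5) | at most 2 of 3 |

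No version offers three separate returns, so completers on listed visits number **0 of 11**.

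**Visit windows.** In v1.0, Day 42 ± 2 ends on Day 44 and Day 84 ± 5 begins on Day 79. No visit is listed on Days 45-78, which removes week 8 as well as week 10. The v2.2 window row is broken in the text available. If its ± 7 days applies to Days 60 and 90, the windows are Days 53-67 and 83-97, which leaves Days 68-82 uncovered; neither 70 nor 71 falls inside. The v3.1 table has no window row. Lending it ± 7 days gives the same result.

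**Sensitivity to a tolerance around week 10.** The SAP states none. With ± 3 or ± 7 days around Day 70 (67-73 or 63-77), no nominal visit day of any of the three versions qualifies. Under the assumed v2.2 window, only a late Day 60 visit could enter: on Day 67 under ± 3, or on Days 63-67 under ± 7. It would then no longer serve as a separate week-8 return.

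**v4.0.** No visit carries a week number. Protocol 5.5 says: "The duration of OP 1 varies. If complete wound closure is obtained during Cycle 1, OP 1 ends when the wound(s) re-open". A subject whose wound closes early in Cycle 1 moves to home imaging, so whether any clinic visit falls in weeks 8, 10 and 12 depends on how dosing goes. The day list for the Investigator's assessment in Protocol 7.3 (15, 30, 45, 60, 90) has no Day 70 either.

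**The case against.** The strongest reply is that little depends on this. SAP 5.1.1 and 5.1.3 do not refer to the 7.1 rule, so no population, estimate or test changes; what changes is one count and one listing in a pilot study without a sample-size calculation. That stands, and it limits the point to reporting.

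The PP definition and the 7.1 category can also coexist formally, because they are two separate definitions. That stands too: the mismatch is an inconsistency of presentation. A reader might infer that the PP population must be empty, but the documents do not support this, since PP never cites the week-8, -10 and -12 rule.

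A third reply is that subjects may in fact have been seen near week 10, at an unscheduled visit, an on-site dosing visit, or a visit after rolling over to a later version (Protocol 1.6 mentions such subjects). Only the schedules of v1.0 to v3.1 are at hand, not the full protocols. Hence the qualifier *on listed visits alone*. But a definition that adherent subjects can meet only through visits outside the plan is still the wrong definition.

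Finally, home images about twice a week could supply wound areas at week 10. They do not rescue the completer rule, which speaks of returning and does not say that an image counts. They do matter for efficacy. A reader might infer from the missing visits that the week-10 CMH stratum has no data. That goes too far: home imaging is described for v2.2, v3.1 and v4.0, and Protocol 10.5.3 names it as a source. Only v1.0 lists imaging at week 12 alone among the three weeks.

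**Conclusion.** The completer rule in SAP 7.1 is wrong as written for the trial it describes. On listed visits, 0 of the 11 subjects under v1.0, v2.2 and v3.1 can satisfy it, and v4.0 has no visits to which it can be applied directly. The consequence is a misleading disposition table and a listing that asks for reasons that do not exist. It should be corrected, but it does not threaten the efficacy comparison.

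The result rests on nominal visit days and holds under either day count. It does not need the v2.2 ± 7-day reading, which is an assumption. It does not claim that all 11 will be non-completers in the data, since extra visits in the right weeks could alter individual cases.

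The unwritten mapping of visits and images to the CMH weeks is a secondary, minor gap: a rule is missing, and no stated rule is in error. The LOCF rule in SAP 6.3 does not fill it, because it replaces only values after the last one observed. A v1.0 subject seen on Day 84 would still have nothing at weeks 8 and 10.

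**What to change.** **Completion (SAP 7.1).** Replace the rule with one that follows each version's schedule:

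1. At least one administration plus the Day 84 visit (v1.0), the Day 90 visit (v2.2 and v3.1) or the visit three months after Cycle 2 (v4.0). The shading that marks optional v2.2 visits cannot be seen in the text, so confirm that Day 90 is a required visit there.
2. State how a v4.0 subject is classed if Cycle 2 is never triggered, since Observation Period 1 has no maximum length. One option is to count the subject as completing if still under observation, without withdrawal, on a named study-end date.
3. Show roll-over before the final visit as its own category.
4. Say whether the PP phrase about completing as planned means this same rule.

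**Week mapping (minor).** For weeks 8, 10 and 12, state one non-overlapping day window per week, the day from which days are counted, the permitted image sources, and one rule for choosing among several images. Apply it consistently, with no override for the Day 60 visit; an override would bring the ambiguity back whenever that visit falls in the week-10 window. Disclose that v1.0 lists imaging at week 12 only among these weeks, and that the rule was set after the partial analysis.

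**Cost.** SAP wording and a little programming, with no new data. Some images will go unused under any selection rule.
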